#### 14.1.1 Glossary

##### *Adverse Drug Reaction (ADR)*

In the pre-approval clinical experience with a new medicinal product or its new usages, particularly as the therapeutic dose(s) may not be established, all noxious and unintended responses to a medicinal product related to any dose should be considered adverse drug reactions. The phrase “response to a medicinal product” means that a causal relationship between a medicinal product and an adverse event is at least a reasonable possibility, i.e., the relationship cannot be ruled out.

##### *Adverse Event (AE)*

An AE is any untoward medical occurrence in a patient or clinical investigation subject administered a pharmaceutical product and that does not necessarily have a causal relationship with this treatment. An AE can therefore be any unfavorable and unintended sign (including an abnormal laboratory finding), symptom, or disease temporally associated with the use of a medicinal (investigational) product, whether or not related to the medicinal (investigational) product.

##### *Serious Adverse Event (SAE) or Serious Adverse Drug Reaction (Serious ADR)*

Any untoward medical occurrence that at any dose:

- Results in death,
- Is life-threatening, i.e., an event which, in the view of the Investigator, places the subject at immediate risk of death from the event as it occurred (it does not include an event which hypothetically might have caused death if it were more severe)
- Requires inpatient hospitalization or prolongation of existing hospitalization,
- Results in persistent or significant disability/incapacity,
- Is a congenital anomaly/birth defect (if exposure to product just before conception or during pregnancy resulted in an adverse outcome in the child), or
- Is an important medical event that may jeopardize the subject or may require medical intervention to prevent one of the outcomes listed above.

Symptoms or medically significant laboratory or instrumental (e.g., electrocardiographic) abnormalities of a pre-existing disease, such as cancer or other disease, should not be considered an adverse event. However, the occurrence of new symptoms, or laboratory or instrumental abnormalities, as well as worsening of pre-existing symptoms, are considered adverse events.

*Unexpected Adverse Drug Reaction*

An Unexpected Adverse Drug Reaction is an adverse event, the nature or severity of which is not consistent with the applicable product information (e.g., Investigator's Brochure for an unapproved investigational product or Package Insert/Summary of Product Characteristics for an approved product).

*Non-Serious Adverse Event*

A non-serious adverse event is any adverse event that does not meet the criteria listed above for a serious adverse event.

14.1.2 *Data Collection*

For each event, record the following information on the Adverse Event section of the Case Report Form:

- **Classification of the Event:** Classify the event as either serious or non-serious
- **Description of Signs or Symptoms:** Whenever possible, record a specific diagnosis for the event. If a diagnosis cannot be made, then record each sign or symptom separately, e.g., record nausea and vomiting as two events. If multiple episodes of an event occur, separated by an appropriate time interval to justify considering the subsequent episodes as a repeat occurrence, record each episode separately on the Case Report Form.
- **Onset Date and Time:** Record the date and time the event started. If a change from baseline/previous evaluation in a laboratory test is reported as an adverse event, record the start date as the date of collection of the first lab sample that shows the change.
- **Stop Date and Time:** Record the date and time the event resolved. If a change from baseline/previous evaluation in a laboratory test is reported as an adverse event, record the stop date as the date of collection of the first sample that shows a return to the previous level.
- **Intensity:**
  1. **Mild:** Event not resulting in disability/incapacity, which resolves without treatment.
  2. **Moderate:** Event not resulting in disability/incapacity, which requires treatment.
  3. **Severe:** Event resulting in temporary and mild disability/incapacity, which requires treatment.
- **Relationship to the Study Agent:** Every effort should be made to determine the cause of each adverse event. The correlation between the study agent and the adverse event should be classified as follows:
  1. **Probable**
    - a) The event follows a reasonable temporal sequence from administration of the study agent;
    - b) The event follows a known response pattern to the study agent;
    - c) The event cannot be reasonably explained by:
      - the known characteristics of subject's clinical state, or
      - by other therapy administered, or
      - by the diagnostic/interventional procedure;
    - d) There is evidence of partial or complete disappearance of the event after withdrawal of the product (positive de-challenge)

2. **Possible**
- a) The event follows a reasonable temporal sequence from administration of the study agent;
  - b) Causation of the event by the study agent cannot be excluded;
  - c) The event follows a known response pattern to the study agent but the event could have been produced by:
    - the subject's clinical state, or
    - other therapy administered, or
    - a diagnostic/interventional procedure.
3. **Unlikely**
- a) The adverse event follows a reasonable temporal sequence from administration of the study agent;
  - b) Other reasons are more likely to be the cause of the adverse event, based on the present knowledge of the
    - disease under treatment, or
    - other therapy administered, or
    - study drug;
  - c) A causal relationship between the adverse event and the study drug cannot be ruled out with certainty.
4. **Not Related** The event is either a pre-dose event or is definitely due to causes separate from the administration of the study agent, i.e.,
- documented pre-existing condition
  - technical and/or manual procedural problems
  - concomitant medication
  - subject's clinical state.

• **Action Taken, in relation to treatment of the AE:**

- 0. **None**
- 1. **Drug treatment required** (a medication was prescribed or changed; record on the Concomitant Medication section of the Case Report Form)
- 2. **Non-drug treatment required** (a non-drug treatment was prescribed or changed; record under "Comments" in the Adverse Event section of the Case Report Form)
- 3. **Hospitalization or prolonged hospitalization** (fill out an SAE report)
- 4. **Diagnostic or clinical test(s) conducted** (attach a copy of the results to the Case Report Form)
- 5. **Subject discontinued from the study**

- **Action taken with study treatment**

0. **Dose not changed**
1. **Drug interrupted**
2. **Drug withdrawn**
3. **Not applicable**

- **Subject Outcome:**

1. **Recovered without sequelae**
2. **Recovered with sequelae** (describe the sequelae under “Comments” in the Adverse Event section of the Case Report Form)
3. **Not Recovered, event on-going** (follow the subject until a definite outcome can be determined. When follow-up data are collected, report follow-up information under “Comments” in the Adverse Event section of the Case Report Form; if event is serious, fill in a follow-up Serious Adverse Event Report)
4. **Died** (list primary cause of death under “Event Description” of the Adverse Event section of the Case Report Form; if available, attach a copy of the autopsy report to the Case Report Form and send a copy to the Sponsor)

- **Comments:**

Provide other pertinent clinical information and observations under “Comments” in the Adverse Event section of the Case Report Form. For example, record predisposing or contributing conditions, such as previous history, concomitant diseases or medications, and/or procedural risks.

#### 14.1.3 *Subject Follow-up*

Every attempt should be made to follow the subject until the adverse event has resolved or until the Investigator determines the subject has returned to an acceptable state of health.

#### 14.1.4 *Reporting Serious Adverse Events (SAEs)*

The Investigator must report **all serious adverse events within 24 hours**, irrespective of the relationship to study medication, to the CRO, by fax or by e-mail (as back-up option), completing the appropriate reporting form. The CRO will then forward this information to EryDel within one business day of receipt. The names of the CRO contact will be communicated to the investigators by the CRO prior to the start of subject enrollment.

The minimum information required for an initial report of a Serious AE is as follows:

- Sender of report (name, address of Investigator, site number),
- Subject identification (screening number),
- Protocol number,
- Reportable event.

All SAE reports and any case of overdose leading to an AE or SAE must be faxed using the appropriate reporting form to the following number within 24 hours:

**Materiovigilance and Pharmacovigilance Unit**

In case of fax failure, all sites can use the following email address as back-up option:

Email: PPD

In case of death, a comprehensive narrative report of the case should be prepared by the Investigator and sent to the CRO by mail together with the Serious AE Form, retaining a copy on-site. If an autopsy is performed, a copy of the autopsy report should be actively sought by the Investigator and sent to the CRO as soon as available. A copy of the autopsy report will be retained on-site.

A follow-up Serious Adverse Event Report will be completed by the Investigator if important follow-up information (i.e., diagnosis, outcome, causality assessment, results of specific investigations) are made available after submission of the initial form. The follow-up form will be sent to the CRO as described above.

If the Investigator becomes aware of any deaths or Serious Adverse Events after the end of the 60-day follow-up window established in the protocol following investigational product administration, they will be reported to the CRO as described above.

**14.2 Safety Reporting to Investigators, IRBs/IECs, and Regulatory Authorities**

The Sponsor or their designee will be responsible for reporting all SAEs to regulatory authorities, investigators, and Independent Ethics Committees / Institutional Review Boards (IRBs/IECs), as applicable, in accordance with national regulations for the United States. For all active investigators located in the United States, the Sponsor or their designee will prepare an expedited report for all SAEs that are unexpected and potentially related to the study drug, and copies will be distributed according to all applicable laws and regulations. The investigational site also will forward a copy of all expedited reports to their IRB/IEC.

**14.3 Reporting Overdose**

If the investigational site staff administering the study medication reports that a subject was given more than the specified dose of study medication, this will be considered an overdose and must be reported immediately to the Investigator. Any instance of overdose, whether symptomatic or not, must be communicated to the CRO within 24 hours and be fully documented as a Serious Adverse Event. Details of any signs or symptoms and their management should be recorded including details of any antidote(s) administered.

**14.4 Pregnancy**

This study will exclude pregnant and breast-feeding patients, and females of childbearing potential, unless they are practicing adequate contraception, as determined by their Health Care Provider. As a further precaution, a serum pregnancy test will be performed at Months 6, 12 and safety follow up visits for all young women who have had a menstrual period within the past year. Results of the pregnancy tests at IEDAT-02-2015 final visit must be negative for the patient to be randomized to treatment.

If a patient becomes pregnant during the study, she will be discontinued from the study immediately. Patients and their parents/caregivers should be instructed to notify the Investigator if it is determined that, after completion of the study they have become pregnant, either during the treatment phase of the study or within 30 days of completing the study. Whenever possible a pregnancy should be followed to term, any premature terminations reported, and the status of the mother and child should be reported to the CRO or EryDel after delivery.

Based on the estimated half-life of dexamethasone given with the EDS, i.e. less than 4 days, a period of one month of continued contraception should follow after study conclusion or early termination due to any reason.

#### 14.5 Independent Data Safety Monitoring Board

An independent Data Safety Monitoring Board (DSMB) will be established by EryDel to review the safety of all patients enrolled in this trial, on an ongoing basis. No EryDel employee or investigator involved in the EDS clinical studies will be a voting member of this board. The DSMB will regularly review the safety data as it accrues.

The Board will be regularly notified of the occurrence of any fatal or life threatening events immediately (within 7 calendar days) and any other serious adverse events within 15 calendar days. The Board will also receive updates on any adverse dropouts on a regular basis (once per month). The Board will have access to the safety data including serious AEs and adverse dropouts, as well as clinically significant abnormal laboratory tests, vital signs and ECGs at periodic intervals.

The DSMB will review all of the safety data on an ongoing basis, with special emphasis on the incidence and severity of steroid related events, new infections, and serious AEs and deaths, in addition to the standard safety parameters. After reviewing the emerging safety profile for EDS-EP, the Board will make a recommendation to EryDel to (a) amend the ongoing study (e.g., increase safety monitoring, modify dosing), (b) terminate the EDS program (e.g., the EDS-EP safety profile is unacceptable), (c) continue the clinical program as designed. The current study protocol will not be amended or changed (this includes the study design and entry criteria) unless mandated by the emergingsafety profile of EDS-EP.

Details of the DSMB charter (separate document) will be submitted to regulatory authorities, and will be available to IECs/IRBs upon request.

## 15 SUBJECT COMPLETION AND DISCONTINUATION

### 15.1 Definitions

'Discontinuation' will refer to any subject who does not complete the full 12 months ( $\pm 30$  days) of this extension.

### 15.2 Procedures for Handling Withdrawals

In the absence of a medical contraindication or significant protocol violation, every effort should be made by the Investigator to keep the patient in the study. All efforts should be made to report the observations as thoroughly as possible at the time of the patient's withdrawal, with an explanation of why the subject is withdrawing from the study.

The criteria for discharging a patient from the study are listed below. The Investigator must indicate the primary reason (only one can be reported) for discontinuation, as well as the date when the decision was made; these will be specified on the 'End of Study' form.

A patient may be withdrawn from study participation if:

- Any hypersensitivity or allergic reaction, clearly linked to the study medication, has occurred;
- the patient experiences an AE sufficiently severe, in the opinion of the investigator, that it contraindicates the patient continuing in the study;  
*If the patient experiences a systemic illness considered unrelated to the study medication, it still must be reported as an AE.*
- the patient/caregiver withdraws consent (e.g. subject refuses to have any more blood samples taken for the EDS process; in this instance a specific reason must be recorded by the investigator);
- a major protocol deviation that jeopardizes the continued well-being of the patient or poses an risk to the patient's health;  
*If the patient is able to abstain in the future from activities/behaviors that constituted a major protocol violation, the patient should be allowed to continue.*
- the patient is lost to follow-up, i.e., the subject did not return to the clinic, and attempts to contact the subject were unsuccessful. Attempts to contact the subject must be documented;
- the Sponsor, IEC/IRB, or regulatory agency terminates the study.

Dropouts will not be replaced.

The Investigator may terminate a patient's study participation at any time during the study if a patient meets the study termination criteria described above. In addition, a patient or his/her parent/guardian may discontinue the patient's participation without giving a reason at any time during the study. Should a patient's participation be discontinued, the primary reason for termination must be recorded. For patients who discontinue prior to Month 12, an attempt should be made to perform the safety follow up visit on the patient, and to follow up on any safety issues until resolution.

Patients who discontinue prematurely should be followed up for 60 days after their final infusion regarding the occurrence of any Serious Adverse Events.

## 16 STATISTICAL METHODS

### 16.1 Analysis of Efficacy

#### *Primary Endpoint*

To monitor and evaluate the long-term safety and tolerability of EDS-EP in AT patients.

#### *Exploratory Endpoint*

To evaluate the long term effect of EDS-EP in treating CNS symptoms as measured by the “Modified” International Cooperative Ataxia Rating Scale (mICARS), Clinical Global Impression of severity and change (CGI-S/C)

#### *Secondary Endpoint*

To evaluate the long-term effect of EDS-EP on health related Quality of Life (QoL; EQ-5D-5L scale).

### 16.2 Statistical Methods

#### 16.2.1 *Sample Size*

There is no formal sample size calculation, as the sample size is dependent on the number of patients who complete the double-blind extension study (Protocol IEDAT-02-2015), express the desire to continue treatment with the investigational drug, and meet the selection criteria defined in [Section 9.2](#) of the Study IEDAT-03 protocol. It is expected that a maximum of 150 patients will enter this open-label extension.

The following analysis sets will be used:

- 1) *Efficacy Population (EP)*: All patients who enter study IEDAT-03, have a baseline efficacy assessment in study IEDAT-03, and who received at least one dose of study medication and had at least one post-baseline efficacy assessment of the primary efficacy variable in this extension study.
- 2) *Safety Population (SP)*: All subjects who receive a dose of study medication, and have at least one post-dose safety assessment will be included in the safety analyses.

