### Exploratory Objective:

- To evaluate the long term effect of EDS-EP in treating CNS symptoms as measured by the “Modified” International Cooperative Ataxia Rating Scale (mICARS), and Clinical Global Impression of severity and change (CGI-S/C)

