### Secondary Objective:

- To evaluate the long-term effect of EDS-EP on health related Quality of Life (QoL; EQ-5D-5L scale).

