#### 11.4.2 Baseline visit (Visit 1/ Day 0)

Final evaluations for IEDAT-02-2015 study (Visit 15/Month 12) will serve as baseline evaluations for patients continuing in IEDAT-03-2018 study. The following "baseline" assessments for IEDAT-03-2018 will be done as part of the final Visit 15 evaluation in Study IEDAT-02-2015: physical/neurological examination; 12-lead standard ECG; laboratory evaluations [including hematology, clinical chemistry, urinalysis, serum pregnancy test (women of childbearing potential); special laboratory tests: HbA1c, CD4+ lymphocytes count and CRP]; assessment of physical development, sexual maturation, and the effect of treatment with dexamethasone on these aspects (Tanner scale); ICARS; CGI-S; CGI-S; EQ-5D-5L; C-SSRS; BMD; review of AEs and concomitant medications.

- a) Obtaining written informed consent (before any study procedures)
- b) Check of the demographic information, medical history, previous and concomitant medications, ongoing adverse events and non-drug therapies and procedures (demographic information, medical history rolled over from IEDAT-02-2015 eCRF)
- c) Vital signs [including height and weight measurements in triplicate at baseline; calculation of BMI, temperature (oral or tympanic, according to the specific medical practice of the Center), pulse, systolic and diastolic BP, and respiratory rate].
- d) Hemolysis panel (including urinalysis), on the diverted blood samples (see Section 11.5)

Patients providing informed consent or assent and meeting the eligibility criteria will receive study treatment prepared and administered as follows:

- e) 1 mL blood collected, after blood diversion (see Section 11.5), for aerobic culture
- f) Autologous blood collection for EDS processing
- g) Addition of the assigned study medication (DSP) to the EDS process
- h) Upon completion of the EDS process, fill the satellite sample bag CCI [REDACTED] if no other samples but the ones for sterility culture test will be collected).
- i) Study treatment administration by IV infusion, within 30 min after the EDS process has been completed.
- j) CCI [REDACTED]  
[REDACTED]  
[REDACTED]  
[REDACTED]  
[REDACTED]  
[REDACTED]  
[REDACTED]  
[REDACTED]

Before the EDS-EP infusion, patients (women of childbearing potential) must undergo a pregnancy urine test. All patients should undergo assessment of prior and concomitant medication and AEs.

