## 12 EFFICACY EVALUATIONS

### 12.1 ICARS

#### 12.1.1 *Description of the ICARS*

The primary efficacy endpoint in the AT study will be the mean change from baseline to endpoint (Month 6 or early discontinuation) in the total score on the 'Modified' International Cooperative Ataxia Rating Scale (ICARS).

The ICARS (Trouillas et al, 1997), the most frequently used clinician-(neurologist) rated measure in patients with ataxias, was developed by a Committee of the World Federation of Neurology to help standardize common manifestations of syndromes that lead to cerebellar dysfunction. The ICARS is a 100-point, semi-quantitative scale offering a compartmentalized quantification of the following 4 sub-scores: Posture and Gait Disturbances (34 points), Kinetic Functions (52 points), Speech Disorders (8 points), and Oculomotor Disorders (6 points).

The complete ICARS will be rated in the current study; however, for the primary efficacy endpoint, the 'Modified' ICARS will be used. The 'Modified' ICARS excludes all of the Oculomotor Disorders items (items 17-19) and items 8-12 in the Kinetic Functions domain, as these items do not directly contribute to functioning.

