#### Full Analysis Set (FAS)

The Full Analysis set comprises *all patients who enter study IEDAT-03, have a baseline efficacy assessment in study IEDAT-03, and who received at least one dose of study medication and had at least one post-baseline efficacy assessment of the ICARS in this extension study.*

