### CGI-C

The results of the CGI-C assessments are presented in a listing together with the categories based on the SAF.

*For the CGI-Change, the proportion [n(%)] of patients rated as improved, as well as those showing no change or worsening, at each time-point will be calculated. This analysis is performed on the FAS as described in section 8.1 and repeated for the subgroups Age (<10 years, ≥10 years) and Region (India; Europe, Australia, Tunisia; United States).*

The CGI-C scores are plotted over time within stacked bar charts on the FAS.

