### EQ-5D-5L

The individual items of the EQ-5D-5L are listed including the values of the VAS, as well as the EQ-5D-5L index and its change from baseline. The listing is presented for patients in the SAF.

The EQ-5D-5L index at baseline and each relevant follow-up visit (every 6 months), and the change from OLE-IEDAT baseline and from ATTeST baseline to each relevant follow-up visit are summarized using summary statistics appropriate for continuous data as described in section 8.1. These summary statistics on the change from ATTeST baseline to each relevant follow-up visit are repeated for the subgroups of placebo patients and non-placebo patients of the ATTeST study. These summary statistics are presented for the FAS.

For the FAS, the mean EQ-5D-5L index is plotted over time with a trend line.

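### The one efficacy set requires a post-baseline ICARS, so a patient without one drops out of every EQ-5D-5L and CGI summary table and figure

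*Protocol*

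**What the plan says.** Protocol 16.2.1 has one efficacy set and one safety set. The efficacy set needs entry into the extension, a baseline efficacy assessment, at least one dose, and that the patient "had at least one post-baseline efficacy assessment of the primary efficacy variable in this extension study". That section does not name the variable. Protocol 12.1.1 does, by making the Modified ICARS the primary efficacy measure: "The primary efficacy endpoint in the AT study will be the mean change from baseline to endpoint". The SAP is explicit: a Full Analysis Set (FAS) patient must have "had at least one post-baseline efficacy assessment of the ICARS in this extension study".

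SAP 10.6.1 applies the FAS to the other scales too. For CGI-C: "This analysis is performed on the FAS as described in section 8.1". For EQ-5D-5L: "These summary statistics are presented for the FAS". CGI-S is treated the same way, and the output lists in SAP 12.1 and 12.2 agree. No endpoint-specific set is defined, and SAP 10.6.1.2 plans no sensitivity analysis.

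On rank, the protocol's only secondary objective is quality of life: "To evaluate the long-term effect of EDS-EP on health related Quality of Life (QoL; EQ-5D-5L scale". The ICARS and CGI belong to its exploratory objective, which opens "To evaluate the long term effect of EDS-EP in treating CNS symptoms as measured by the". SAP 3.1 moves the ICARS and CGI to secondary and EQ-5D-5L to tertiary. SAP 3.6 does not list this as a change from the protocol. SAP 3.4 puts EQ-5D-5L under a tertiary heading while the sentence below still calls the objective secondary.

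**The concern.** Whether a patient counts in one instrument's summary is decided by whether a different instrument was completed. Under the protocol's ranking, an exploratory scale controls who is summarised for the secondary objective.

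The scales can be missing separately. The ICARS is rated by the same trained and certified site neurologist throughout (Protocol 12.1.3). The CGI-C rater must be someone else (12.2). EQ-5D-5L is answered by the patient or caregiver (12.3). If the neurologist's rating is missing at every visit, quality-of-life and global-impression data already collected leave the summaries.

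The condition does no analytic work here. Efficacy is purely descriptive (SAP 8.2), there are no hypothesis tests (SAP 9), and SAP 8.1 already reports the number of non-missing values for continuous variables. SAP 3.6 also dropped the comparable requirement for a post-dose assessment from the safety set. The efficacy condition was kept and applies to unrelated scales.

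**Working it through.** The plan gives no figure to reproduce: 150 is an expected maximum, not a calculation. The check is a count of planned outputs by analysis set, then an illustration of scale.

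**1. Outputs by set (SAP 12.1 to 12.3)**

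- FAS tables: mICARS 12 + RmICARS 12 + ICARS 6 + CGI-C 6 + CGI-S 6 + EQ-5D-5L 6 = 48.
- FAS figures: mICARS 2 + RmICARS 2 + ICARS 2 + CGI-C 1 + CGI-S 1 + EQ-5D-5L 1 = 9.
- Safety-set listings: ICARS items, ICARS totals, CGI-C, CGI-S, EQ-5D-5L = 5.
- Total: 48 + 9 + 5 = 62, of which 57 depend on the ICARS condition.
- Of those 57, 18 tables and 3 figures summarise a scale other than the ICARS.

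So every efficacy summary table and figure is affected, but the five listings are not.

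**2. Patients left out**

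Let f be the share of patients with a post-baseline EQ-5D-5L or CGI but no post-baseline ICARS. The documents do not give f, so 0-10% is an assumption. The expected number is N × f, and the chance of at least one such patient is 1 − (1 − f)^N. N = 150 is the protocol maximum; N = 75 is half of it, for comparison.

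| f (assumed) | N = 150: expected | chance of at least one | N = 75: expected | chance of at least one |
|---|---|---|---|---|
| 0% | 0 | 0 | 0 | 0 |
| 1% | 1.5 | 0.78 | 0.75 | 0.53 |
| 2% | 3 | 0.95 | 1.5 | 0.78 |
| 5% | 7.5 | >0.99 | 3.75 | 0.98 |
| 10% | 15 | >0.99 | 7.5 | >0.99 |

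**3. Effect on an overall mean**

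If the omitted patients differ from the rest by d standard deviations (SD), the mean moves by about f × d. With d = 0.5 (assumed), this is 0.02 × 0.5 = 0.01 SD at f = 2% and 0.10 × 0.5 = 0.05 SD at f = 10%. The sign is unknown.

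**4. Small columns**

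SAP 6.3 shows seven ATTeST groups, four of them placebo patients switched during that trial. Assume 150 patients with the parent trial's three equal groups and switching thirds (Protocol 7.1.3.4):

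- 150/3 = 50 started on placebo;
- 50/3 ≈ 17 per switch time;
- 17/2 ≈ 8 per dose.

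One loss would be 1/8 = 12.5% of such a column. At f = 0-10%, however, the expected loss per column is only 0 to 0.8 patients.

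**The case against.** The strongest reply is that few patients, or none, may be affected. One ICARS at any post-baseline visit is enough. All the scales are scheduled at the same six-monthly visits (Protocol 11.2), and the ICARS is to be given first (12.5). A patient who discontinues should have the Month 12 evaluations at that point (16.2.6). One who leaves before Month 6 without them has none of these scales, so a new set would recover nothing. A site rater also administers EQ-5D-5L (9.1). The listings keep all the data, and SAP 10.3 lists each FAS exclusion with its primary reason. A common set also keeps the same patients behind each scale. All of this stands. It limits the size of the problem but does not justify the rule.

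A reader might infer four stronger things that the documents do not support.

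- **ATTeST completers are excluded because their baseline lies in the parent trial.** They are not. The protocol designates those evaluations as this study's baseline and says they "will be done as part of the final Visit 15 evaluation in Study IEDAT-02-2015" (11.4.2). SAP 7.1 repeats this.
- **Every efficacy output is affected.** The five listings use the safety set.
- **The ICARS is lost because it must be rated in person, particularly during COVID-19.** The protocol requires a certified neurologist but does not state in-person rating. The pandemic changes are in an appendix that is not in the text available here.
- **The quality-of-life result is flattered.** Nothing shows which way the omitted patients differ.

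Lost CGI data also do not touch the protocol's secondary objective, because CGI is not part of it.

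**Conclusion.** The point holds in a narrow form. By the stated definition, a dosed patient with post-baseline EQ-5D-5L or CGI but no post-baseline ICARS is missing from the 18 tables and 3 figures for those scales. No other efficacy set restores that patient. For EQ-5D-5L this removes the patient from every summary of the endpoint. A screening ICARS, as taken for patients discontinued from ATTeST during the pandemic, does not meet the condition because it is not post-baseline.

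The size is unknown: 0 to 15 patients under an assumed 0-10% of at most 150. The likely effect on an overall mean is slight, about 0.01 to 0.05 SD at 2-10% under the further assumption of a 0.5 SD difference. Minor severity; worth correcting because it is cheap.

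**What to change.** In SAP 6.1 and 10.6.1, summarise each endpoint on all patients dosed in OLE-IEDAT who have at least one post-baseline value of that endpoint in the extension. For change analyses, require in addition only the baseline which that change uses: the OLE-IEDAT baseline as defined in SAP 7.1, or the ATTeST baseline. Pointing the wording to SAP 7.1 also removes any doubt about where the baseline comes from. Show n per endpoint, and record the departure from Protocol 16.2.1 in SAP 3.6. The differing rank of EQ-5D-5L in the two documents can be reconciled in the same edit.

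The cost is a change of SAP wording and one population flag per endpoint, with no new data. The downside is that n may differ slightly between endpoints, as it already can through missing values.
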